6.8.2 Patient Populations Analyzed

The analysis sets that will be used for statistical analyses are as follows:

Intent-To-Treat (ITT): All randomized patients. Patients will be analyzed according to the treatment to which they are randomized. The ITT Population will be the primary analysis set for the efficacy variables.

Per Protocol (PP): Supporting analyses will be conducted on the PP Population, comprising all patients randomized and treated without major protocol violations during the trial. This population will be documented before final database lock.

Safety: All patients who received at least one dose of study treatment. Patients will be included in the analyses according to the treatment they received. The Safety Population will be used in the analyses of all safety endpoints.

6.8.3 General Considerations

The following is an overview of the statistical analysis methods to be used in this study. Details on the statistical analyses will be given in the Statistical Analysis Plan (SAP). Patients will be randomized to one of the following treatment groups in a 1:1:1 ratio:

- **Group 1**: Idarubicin + Cytarabine, OR
- **Group 2**: Idarubicin + Cytarabine plus lower dose CX-01 (0.125 mg/kg/hour), OR
- **Group 3**: Idarubicin + Cytarabine plus higher dose CX-01 (0.25 mg/kg/hour)

Unless stated otherwise, descriptive summary statistics will include frequency counts and percentages for categorical variables and number of observations, mean, standard deviation (SD), median, minimum and maximum and the 1st and 3rd quartiles for continuous variables.

The final analysis will be done when the last patient completes the study treatment, all assessments for disease response, and a Safety Follow-Up Visit approximately 30 days after termination of study treatment. All patients will be followed for OS for at least 18 months. Statistical analysis will be performed using SAS; the version used will be specified in the SAP.

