--	---

	
 • Cytarabine 1.0 gram/m² over 3 hours, every 12 hours on Days 1, 3, and 5. 
Group 3: Cytarabine + higher dose CX-01
 
 • CX-01 given as a 4 mg/kg initial bolus on Day 1, 30 minutes after completion of the first 3-hour infusion of cytarabine, followed immediately by CX-01 0.25 mg/kg/hour as a continuous 24-hour IV infusion on Days 1-5 for a total of 120 hours of continuous CX-01 infusion • Cytarabine 1.0 gram/m² over 3 hours, every 12 hours on Days 1, 3, and 5.
Duration of Treatment:	Patients will receive up to two induction cycles and up to two consolidation cycles of treatment.
Duration of Patient Participation in Study:	Each patient will participate in the study for approximately 18 months from the time of informed consent through final study contact, or until they withdraw from the study or the study is terminated by the Sponsor.
Diagnosis and Main Criteria for Inclusion:	
To be eligible to participate in the study, patients must meet the following criteria:
 
 1. Newly diagnosed, de novo or secondary, previously untreated AML 2. Age 60 or above 3. Eastern Cooperative Oncology Group (ECOG) performance status of 0 to 2 4. Cardiac ejection fraction $\geq 45\%$ (as determined by echocardiography or multi gated acquisition scan) 5. Adequate hepatic and renal function determined by the following laboratory values: 
 • Aspartate aminotransferase (AST) or alanine aminotransferase (ALT) $< 2.5 \times$ upper limit of normal (ULN) • Bilirubin $< 2.5 \times$ ULN • Calculated creatinine clearance by Cockcroft Gault formula > 30 mL/min. 6. Able to provide informed consent and have signed an approved consent form that conforms to federal and institutional guidelines.

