Patients may start consolidation therapy anywhere from 4 to 8 weeks after the start of induction therapy based on treating Investigator judgment. Consolidation will begin no sooner than 28 days from the start of induction therapy.

Subsequent consolidation cycles may begin anywhere from 4 to 8 weeks after the start of the last cycle of consolidation based on treating Investigator judgment.

Patients will receive consolidation therapy in the same treatment group as assigned at randomization, as follows:

Group 1: Cytarabine

- Cytarabine 1.0 gram/m² over 3 hours, every 12 hours on Days 1, 3, and 5.

Group 2: Cytarabine + lower dose CX-01

- CX-01 given as a 4 mg/kg initial bolus on Day 1, 30 minutes after completion of the first 3-hour infusion of cytarabine, followed immediately by CX-01 0.125 mg/kg/hour as a continuous 24-hour IV infusion on Days 1-5 for a total of 120 hours of continuous CX-01 infusion
- Cytarabine 1.0 gram/m² over 3 hours, every 12 hours on Days 1, 3, and 5.

Group 3: Cytarabine + higher dose CX-01

- CX-01 given as a 4 mg/kg initial bolus on Day 1, 30 minutes after completion of the first 3-hour infusion of cytarabine, followed immediately by CX-01 0.25 mg/kg/hour as a continuous 24-hour IV infusion on Days 1-5 for a total of 120 hours of continuous CX-01 infusion
- Cytarabine 1.0 gram/m² over 3 hours, every 12 hours on Days 1, 3, and 5.

6.4.1.1 *Transfusions*

- Red blood cell (RBC) transfusion will be administered according to institutional guidelines
- Platelet transfusions will also be given at the discretion of the treating Investigator based on clinical characteristics and patient need.

6.4.1.2 *Dosing and Method of Administration*

All chemotherapy and CX-01 doses will be calculated based on actual body weight at the beginning of each cycle of induction or consolidation therapy.

Chemotherapy will be administered through a central venous catheter, such as a peripherally inserted central catheter, with two or three independent ports. This catheter may also be used for administration of blood products, IV medications and IV fluids.

CX-01 bolus and continuous infusions may be administered in the same arm through a peripheral IV line; however, must be separate from the central line or port used for chemotherapy.

6.4.1.3 *Preparation of CX-01 Infusion*

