6.5.5 Safety Follow-Up Visit

Patients will complete a Safety Follow-Up Visit approximately 30 days after completion of the last induction or consolidation cycle. See Table 6—1 for clinical assessments performed at this visit. Longer follow-up may be required for patients who do not have an ANC recovery by Day 42 (that is, until the recovery or until a reason for no recovery is diagnosed) after the last induction or consolidation cycle.

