6.5.7 Long Term Follow-Up

After Safety Follow-Up Visit, the relapse and survival data will be collected every 3 months.

Each subject will participate in the long term follow-up for approximately 18 months from the time of informed consent until death or until the end of the study (for the definition of end of study, see Section 6.1).

Investigational sites are expected to make every effort to obtain long term follow-up data. This level of diligence is necessary to ascertain the patient's health status, and thus avoid lost to follow-up status for efficacy assessments. Follow-up may require:

- Permission for study personnel to contact an alternative person (e.g., family, spouse, partner, legal representative, or physician) even if only by telephone
- Permission for study personnel to access and review the patient's medical information from alternative resources (e.g., doctors notes, hospital records)

Attempts to contact patients must be documented in the patient's source documents and in the eCRF. The source documents for OS may be sent remotely to the site Clinical Research Associate for review and verification (ensuring patient identifiers are redacted except for study number and initials).

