Overall survival data will be collected every 3 months until death or until the end of study by the investigational sites. The end of study will occur approximately 18 months after the last patient is randomized. Overall survival data will be collected every 3 months until death or until the end of study by the investigational sites. The end of study will occur approximately 18 months after the last patient is randomized.

A Data and Safety Monitoring Committee (DSMC) will meet periodically to review the safety of the study (see Section 6.6.5 of protocol). Details describing the DSMC process and procedures will be outlined in a separate DSMC Charter.

Adverse events (AEs) will be collected from time of informed consent and continue until 30 days after the last study treatment is administered. Longer follow-up and collection of AEs may be required for patients that do not have an absolute neutrophil count (ANC) recovery within 42 days (i.e., until the recovery or the reason for no recovery is diagnosed) after the last induction or consolidation cycle.

A flow diagram of the study design is shown in Figure 2---1.

[figure not shown]
Statistical Analysis Plan

Version: Final

Date of Issue: 20 March 2018

Cantex Pharmaceuticals, Inc. Protocol No. CNTX-CX-0 I 2015 AML I Covance Study ID: 00000014620 I

Figure 2---1 Study Design

Abbreviations: AML=acute myeloid leukemia

Note: It is expected that approximately 90 patients will be screened to identify 75 patients for randomization.

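### The only defined final analysis falls 12 to 17 months before the last patient completes survival follow-up, and no data cut is set for OS, EFS, LFS or remission duration

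*Protocol*

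**What the plan says.** Protocol section 6.8.3 defines a single final analysis: "The final analysis will be done when the last patient completes the study treatment, all assessments for disease response, and a Safety Follow-Up Visit". The sentence after it reads "All patients will be followed for OS for at least 18 months".

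Other places bear on the timing:

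- **End of study.** SAP section 2.5, repeating Protocol section 6.1: "The end of study will occur approximately 18 months after the last patient is randomized".
- **Start of long-term collection.** Protocol section 6.5.7: "After Safety Follow-Up Visit, the relapse and survival data will be collected every 3 months".
- **Safety visit.** Protocol section 6.5.5: "Patients will complete a Safety Follow-Up Visit approximately 30 days after completion of the last induction or consolidation cycle". The column heading in Table 6-1 counts the 30 days from the last dose instead.
- **Length of treatment.** Protocol synopsis: "Patients will receive up to two induction cycles and up to two consolidation cycles of treatment".
- **Follow-up summaries.** SAP section 7.2 and shells 14.1.2.9 to 14.1.2.11 summarize long-term follow-up status and cause of death to about 18 months.
- **Study report.** Protocol section 8.10 places the clinical study report after completion of the study.

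The SAP gives no cut-off date or event for the time-to-event endpoints. Its section 8, which lists departures from the protocol, leaves the 6.8.3 trigger alone. Protocol section 6.8.2 and SAP section 5 both refer to one final database lock.

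**The concern.** For the last patient, the trigger is reached at the visit after which 3-monthly relapse and survival collection begins. A programmer who follows 6.8.3 would lock and analyse OS, EFS, LFS and remission duration with almost no long-term data from late enrollees. A programmer who follows SAP section 7.2 would wait for about 18 months of follow-up. The two readings give different data sets for named secondary objectives.

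OS is called descriptive, but shell 14.2.19 carries a log-rank comparison with control, so a p-value would rest on whichever cut is taken. The trial is open-label, and an unspecified survival cut leaves its timing open to choice after results have been seen.

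**Working it through.** **The plan's own figure.** The stated power is 71.8% (25 per arm, CR 0.55 versus 0.80, Fisher's exact test, one-sided 0.15). Exact enumeration of the two binomials gives 71.7%, which agrees. CR is settled during induction and re-induction, so the timing question does not touch it.

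**Step 1: when the trigger falls.** Day 1 is the start of induction, taken as the day of randomization. The first consolidation window is "Patients may start consolidation therapy anywhere from 4 to 8 weeks after the start of induction therapy", that is Day 29 to 57. The next is "Subsequent consolidation cycles may begin anywhere from 4 to 8 weeks after the start of the last cycle of consolidation", that is Day 57 to 113. A consolidation course lasts 5 days. The windows are counted from the first induction; counting from a re-induction would move the latest dates by less than a month. Re-induction is assumed to start on Day 15 to 28. Safety visit = last dose + 30 days.

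| Path | Last dose | Safety visit | Short of 18 months (548 days) |
|---|---|---|---|
| Induction only | Day 7 | Day 37 | 511 days |
| Re-induction, 5+2 or 7+3 | Day 19 to 34 | Day 49 to 64 | 499 to 484 days |
| One consolidation | Day 33 to 61 | Day 63 to 91 | 485 to 457 days |
| Two consolidations | Day 61 to 117 | Day 91 to 147 | 457 to 401 days |

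If the visit is counted from the end of a second consolidation cycle that runs to its Day 42 (assumed), it falls on Day 113 + 41 + 30 = 184, which is 364 days short. At 30.44 days per month, the trigger is 1.2 to 6.0 months after the last randomization and the shortfall is 12.0 to 16.8 months.

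**Step 2: patients without 18 months' follow-up at the cut.** Accrual length A is not stated, so uniform accrual is assumed. For a cut c months after the last randomization, the share is min(1, (18 − c)/A). With c from 2.5 to 5:

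- A = 12: 100%
- A = 24: 13/24 to 15.5/24 = 54 to 65%
- A = 30: 13/30 to 15.5/30 = 43 to 52%

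**Step 3: deaths captured.** Assume exponential OS with median m and λ = ln 2/m. The expected proportion dead at a cut c months after the last randomization is

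F(c) = 1 − [exp(−λc) − exp(−λ(c + A))]/(λA).

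The fraction captured is F(c)/F(18).

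- A = 24, m = 14, c = 2.5: 0.483/0.760 = 64%, or about 36 of 57 deaths among 75 patients.
- A = 24, m = 10, c = 5: 0.655/0.860 = 76%.
- A = 12, m = 14, c = 2.5: 0.334/0.691 = 48%.
- A = 30, m = 10, c = 5: 0.702/0.879 = 80%.

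Taking the extremes from Step 1 instead of c = 2.5 to 5 widens 48 to 80% to 42 to 82%: 0.290/0.691 at A = 12, m = 14, c = 1.2, and 0.723/0.879 at A = 30, m = 10, c = 6.0.

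**Step 4: Day 60 and Day 90 mortality.** Patients not yet at Day d when the trigger falls on Day T of the last enrollee number about 75 × (d − T)/(30.44 × A). In the worst case, T = 37:

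- Day 60: 75 × 23/(30.44 × 12) = 4.7 with 12 months' accrual; 2.4 with 24.
- Day 90: 75 × 53/(30.44 × 12) = 10.9 with 12 months' accrual; 5.4 with 24.

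Once T reaches 91, both counts are zero.

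**The case against.** The strongest reply is that the documents do not intend to stop at the early cut. SAP section 7.2 and its shells run to about 18 months, the study report follows completion, and Protocol section 8.2 delivers all data at the conclusion of the study. A reader might infer from 6.8.3 that the later follow-up is never analysed. These places do not support that, because status and cause of death are to be summarized. What remains is that these are disposition tables. They set no cut for the efficacy analyses, and they presuppose data that do not exist at the 6.8.3 trigger.

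A reader might also infer that Day 60 and Day 90 mortality will generally be incomplete. That is too strong. The trigger waits for every patient, so anyone still in consolidation pushes it later, and response assessment can itself run past Day 37. A simulation assumed 24-month uniform accrual, 30 to 70% of patients reaching consolidation, half of those having two courses, and 30% re-induced. Day 60 was incomplete in 2 to 20% of trials (mean under 0.4 patients) and Day 90 in 23 to 54% (mean 0.4 to 1.7 of 75). The effect is small and conditional. It still needs a rule, because shell 14.2.10 reports mortality as a simple proportion with a Fisher test, and neither document says how to count a patient alive but not yet at Day 60 or 90.

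Finally, the time-to-event analyses are descriptive, carry no alpha or event target, and Kaplan-Meier estimation handles censoring. This stands as a limit on the consequence: the estimates would be less mature and less precise. Censoring does not supply the missing events. EFS should suffer less than OS, because failure to remit counts as an event within the first 60 days.

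**Conclusion.** The concern holds as an unreconciled conflict over timing. The only stated trigger comes 12 to 17 months before the last patient completes the promised follow-up, while other sections presuppose data to about 18 months, and no cut is named for OS, EFS, LFS or remission duration. At the stated trigger, roughly half to four-fifths of the deaths expected by end of study would be available. The treatment windows come from the protocol; accrual length, its uniformity, median OS, exponential survival and the re-induction start are assumptions. The primary CR test and its power are unaffected, and mortality to Day 90 is at risk only for a few late enrollees, if those who set the trigger had short treatment paths. The correction should be made, but it does not threaten the trial's main conclusion.

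**What to change.** In Protocol section 6.8.3 and in the SAP, replace the single trigger with two:

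1. **Primary analysis** (CR, composite CR, count recovery, safety, Day 30/60/90 mortality): when the last patient has finished treatment, response assessment and the safety visit, and every patient has reached Day 90 or died.
2. **Final analysis of OS, EFS, LFS and remission duration**, including the OS log-rank comparison: on the end-of-study data cut, about 18 months after the last randomization.

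The SAP should also say which data cut or lock serves each analysis, and its section 8 should record the change.

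The cost is wording plus a second run of existing tables, with no added patients or visits. Waiting for Day 90 delays the primary analysis by at most 90 − 37 = 53 days, and only on the shortest treatment path. The real downside is that final time-to-event results come later.

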6.8.4 Demographics and Other Baseline Characteristics

6.8.4.1 *Patient Disposition*

The number and percentage of patients screened, randomized, and treated will be presented by treatment group. The reasons for patients discontinued from the treatment will be summarized by study stage and treatment group. In addition, the number of patients screened and included in each analyses population will be displayed by center.

6.8.4.2 Patient and Disease Characteristics

Descriptive summaries of demographics and baseline characteristics will be presented by treatment group and overall for the Safety, ITT, and PP Populations. Comparability of the treatment groups with respect to demographic and baseline characteristics will be assessed using the descriptive summaries.

The following demographic data will be summarized:

- Age at Screening (years)
- Race and ethnicity
- Height (cm)
- Weight (kg) at baseline.

The following baseline characteristics will be summarized:

- Stage of AML at diagnosis
- Time since diagnosis
- Baseline blasts in bone marrow (%)
- Baseline peripheral blasts
- ECOG performance status
- Baseline LDH

6.8.5 Medical and Surgical History

Medical and surgical history includes relevant history other than AML. This information will be coded using the version of MedDRA currently in effect at the time of database lock.

6.8.6 Concomitant Therapy

All non-study medications taken during the study will be coded using the World Health Organization Drug Dictionary (WHO-DD) and the Anatomical Therapeutic Chemical classification system. Coding will include the drug class and generic drug name. Non-study medications taken during the study will be categorized as prior medications, concomitant medications, and post treatment medications. Prior medications will be defined as non-study medication with a stop date prior to the first dose of study treatment.

Post treatment anti-AML therapies will be coded and summarized.

6.8.7 Extent of Study Drug Exposure and Compliance

Extent of study drug exposure will be summarized for the entire study treatment period and by cycle. Exposure variables will include duration of study treatment, number of dose reductions, number of treatment delays, number of treatment cycles, and dose intensity relative to dose levels specified in the protocol.

6.8.8 Efficacy Analysis

6.8.8.1 *Primary Efficacy Outcome Measure*

The primary efficacy analysis will be performed on the ITT Population as defined in Section 6.8.2. Fisher exact test will be used to compare the proportion of CRs between each dose and control.

6.8.8.2 *Secondary Efficacy Outcome Measures*

The primary analysis will be repeated using the PP Population as a supportive analysis. Complete response rates and confidence intervals will also be reported for key subgroups (e.g., randomization strata). Analyses of EFS, LFS, time to neutrophil and platelet recovery, and OS will be descriptive. Kaplan-Meier (KM) estimates will be used to estimate the survival distribution for each arm and KM plots will be produced to accompany these analyses. Confidence Intervals will be reported for medians and KM estimates. Duration of response will be analyzed using a similar approach; the analysis will account for the competing risk of death and the survival distributions will be estimated as cumulative incidence functions.

Mortality rate at Day 30, Day 60, and Day 90 will be reported using descriptive statistics in a manner similar to the reporting of the morphologic CR rate. The time to neutrophil and platelet recoveries will be reported using the following descriptive statistics: N, mean, SD, median, minimum, maximum, and the 1st and 3rd quartiles.

6.8.9 Subgroup Analysis

Subgroup analyses will be defined in the SAP. All results from these analyses are deemed to be exploratory. Exploratory analysis will be descriptive.

6.8.10 Safety Analysis

Safety analysis will be descriptive based on the Safety Population and will involve examination of descriptive statistics and individual patient listings for effects of study treatment on clinical safety and tolerability. The safety assessment period is from the first dose of study treatment until 30 days following the last dose of study treatment.

6.8.10.1 *Adverse Events*

All AEs will be categorized by SOC and Preferred Term using the MedDRA dictionary

and graded according to NCI-CTCAE v4.03. Treatment-emergent AE summaries will include NCI-CTCAE Grade 3 or higher AEs, and AEs resulting in discontinuation of study treatment, AEs resulting in death, deaths during the treatment period within 30 days of the last study treatment, deaths reported beyond 30 days that are considered study drug-related, and the incidence of laboratory values with NCI-CTCAE Grades 3 or 4. Particular attention will be upon coagulation parameters and bleeding-related events.

